**CONFIDENTIAL AND PROPRIETARY**

- 
- a- Potential patients will be identified by clinician referrals. All patients will share same recruitment process and procedures
  - b- Only adverse event related to the use of the ECG Belt and/or device malfunctions
  - c- The use of the ECG Belt Research System might add approx. 40 minutes of time to f/u visits for testing parameters, plus 10 min for system set up.
  - d- When 1-week f/u is completed, subject is considered exited from the study unless unresolved system related AEs occur. An unscheduled follow-up visit may be required.
  - e- Special attention to: ACE/ARB, beta blockers, diuretics, and anti-arrhythmic use

#### **4.6 Primary Endpoints**

The primary endpoints will be

- ECG Belt analysis of Standard Deviation of Activation Times (SDAT) of LBBAP compared to native conduction
- ECG belt analysis of Left Ventricular activations times (LVAT) of LBBAP compared to baseline
- ECG belt analysis of SDAT and LVAT of HOT-CRT compared to baseline
- ECG belt analysis of QRS duration at baseline compared to various LBBAP options
- Comparison of above parameters of LBBP to historic biventricular or RV pacing

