## CONFIDENTIAL AND PROPRIETARY

---

endocardial pacing in addition to conduction system pacing without a lead in the LV endocardial cavity.

The electrophysiological and ECG characteristics of LBB Pacing has not been well described. The ECG Belt can help assess the difference between baseline, RV pacing, LBBAP and His (or LBBAP) Optimized CRT (HOT-CRT) and understand the electrical synchrony and characteristics of physiologic pacing.

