### **3 OBJECTIVES**

#### **3.1 General Objective**

The objective of the study is to assess the utility of ECG Belt to understand the conduction and ECG characteristics of LBBAP and HOT-CRT and compare with preexisting data in traditional CRT and RVP.

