#### **3.2 Specific Objective**

- To demonstrate and establish electrical resynchronization using ECG Belt Research System in LBBP and HOT-CRT.
- To assess ECG Belt derived native conduction parameters and compare them to LBBAP and HOT-CRT.
- To compare with historic ECG belt parameters obtained for right ventricular pacing/ Biventricular pacing in prior studies (Bank et al)

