### **CONFIDENTIAL AND PROPRIETARY**

---

Eligible patients would have successfully undergone LBBAP using Medtronic 3830 lead and C315His sheath. LBBAP will be confirmed at implant using left bundle potentials recorded from the lead, ECG morphology during unipolar and bipolar pacing, peak LV activation time and lead depth in the LV septum by contrast at implant and 2D echo post-implant.

ECG belt would be used to record ECG during baseline rhythm, LBBAP in unipolar and bipolar configurations and / or during HOT-CRT using HBP or LBBAP. These ECG belt characteristics would then be compared with baseline and existing data on RV pacing and traditional Biventricular pacing.

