### **4.2.2 Inclusion Criteria**

The following is the inclusion criteria for the ECG Belt study:

1. Patients > 18 years of age
2. Patient has a previously implanted LBBAP lead for bradycardia indication or heart failure indication with one of the following at Geisinger within the last 5 years:
  - LBBAP
  - LBBAP+LV lead
  - HBP+LV
3. Patient is willing to comply with all study procedures and be available for the duration of the study.

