**CONFIDENTIAL AND PROPRIETARY**

- 
- Native conduction
  - RV pacing if available
  - Bipolar LBBAP
  - Unipolar LBBAP – nonselective and selective (different outputs)
  - Fusion pacing with native conduction at different AV delays
  - HOT-CRT
    - Native conduction
    - HBP / LBBAP
    - HOT-CRT
    - AV delay optimization.
  - Medtronic Device (pacemaker/ICD) based Holter recording during the ECG belt recording\*\*
  - 12-lead ECG (Rhythm Strips)
  - Adverse Events related to ECG Belt

\*The use of the ECG Belt Research System may add approximately 40 minutes of time to follow-up visits for testing parameters, plus 10 minutes for the application of the ECG Belt and System set-up.

\*\*The DR220 Digital Recorder (NorthEast Monitoring, Inc, MA, USA) is a Holter monitor that is designed to facilitate the ambulatory cardiac monitoring and is intended for use with Medtronic System-B compatible implantable pulse generators, implantable cardiac defibrillators, and cardiac resynchronization therapy devices and implantable cardiac monitors. The Holter monitor will be used in accordance with its labeling. Only trained study personnel should apply the monitors. The data obtained by monitoring is not analyzed at the time of the recording. After the recording is complete, the data must later be returned and analyzed at Medtronic. **No personal information will be entered and collected by DR220 recorder.**

For the purposes of this study, the Holter will be used during the in-office monitoring and will be removed at the conclusion of the monitoring. Each patient will have one DR220 Holter monitors collected during the study.

The Holter Recorder has application for any subject with a Medtronic IPG. For the purposes of this study, the intended use of the Holter Recorder is to acutely uplink continuous EGM signals that will be collected by the IPG in Holter mode.

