#### **4.7 Secondary Endpoints**

There are no secondary endpoints.

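### RV pacing is to be recorded where possible in the same session as LBBAP, but the plan lists no within-patient contrast of the two and takes its RV comparator only from prior data

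*Combined protocol and SAP*

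**What the plan says.** Section 4.5 (Visit 1, LBBP recording list) has the belt record native conduction, "RV pacing if available", bipolar LBBAP, unipolar LBBAP and fusion pacing in one session. The separate HOT-CRT list does not include RV pacing.

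Section 4.6 has five primary endpoint bullets. Four compare a pacing mode with native conduction or baseline. The fifth is "Comparison of above parameters of LBBP to historic biventricular or RV pacing". Section 4.7 adds: "There are no secondary endpoints".

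Three other places give the source of the RV comparator:
- Section 3.1: "compare with preexisting data in traditional CRT and RVP"
- Section 3.2: "To compare with historic ECG belt parameters obtained for right ventricular pacing/ Biventricular pacing in prior studies"
- Section 4.1: "These ECG belt characteristics would then be compared with baseline and existing data on RV pacing and traditional Biventricular pacing"

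Section 4.8 repeats the comparison with historic values. It also promises descriptive summaries of every variable. It names t-tests and an open-ended list of non-parametric tests, with the median and rank sum tests as examples. It says that the study is exploratory and that test results are not conclusive but will feed the design of a larger study.

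Section 4.2.2 admits patients with a "previously implanted LBBAP lead for bradycardia indication or heart failure indication".

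**The concern.** A patient who has both an RV and an LBBAP recording serves as their own control. The difference between the two recordings is free of differences between study populations. The plan intends to collect such pairs but lists no use for them beyond the general summary tables. It makes the RV comparison against other studies instead.

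That comparison is open to case mix. The trial admits bradycardia and heart-failure indications. The one source cited for the historic values is, by its title, a study of patients with cardiac resynchronization therapy. Section 4.8 refers to prior studies in the plural, so other sources are possible, but none is described and no matching or adjustment is planned. A difference between the patient groups could then enter the planning of the larger study as if it were an effect of pacing.

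**Working it through.** **Text check.** The plan states no power, alpha or derived sample size, so there is no figure to reproduce. The question is whether any planned comparison sets LBBAP against RV pacing recorded in the same patients.

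- Primary endpoints (4.6): 0 of 5. Only the fifth names RV pacing.
- Secondary endpoints (4.7): none exist.
- Specific objectives (3.2): 0 of 3. The third names RV pacing and takes it from prior studies.
- Comparisons listed in 4.8: none. RV pacing appears only as a historic value.
- Section 2 names RV pacing among the states the belt can help compare, but as rationale. No objective, endpoint or listed analysis carries it forward.

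The fifth endpoint could be read with the word historic attached only to biventricular pacing, which would leave RV pacing open to in-study recordings. Sections 3.1, 3.2, 4.1 and 4.8 each place RV pacing in earlier data, so that reading fails.

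**Precision, as illustration.** The unit is the between-patient SD, taken as equal in all groups. The only input from the documents is the sample of about 20 (4.2.1). The number of pairs n, the within-patient correlation rho and the historic sample size N are assumed.

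Paired 95% half-width = t(0.975, n−1) × sqrt(2(1−rho)/n). For example, n = 10 and rho = 0.5 give 2.262 × sqrt(0.1) = 0.72.

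| Pairs n | rho = 0.7 | rho = 0.5 | rho = 0.3 |
|---|---|---|---|
| 3 | 1.92 | 2.48 | 2.94 |
| 5 | 0.96 | 1.24 | 1.47 |
| 10 | 0.55 | 0.72 | 0.85 |
| 20 | 0.36 | 0.47 | 0.55 |

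Historic 95% half-width with 20 LBBAP patients = t(0.975, 18+N) × sqrt(1/20 + 1/N). This is 0.58 for N = 30, 0.53 for N = 50 and 0.49 for N = 100.

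The smallest n at which the paired interval is no wider than the historic one, for rho = 0.7 / 0.5 / 0.3, is 10 / 14 / 19 with N = 30 and 13 / 19 / 26 with N = 100.

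**Trade-off with bias.** If case mix shifts the historic comparison by d SD, its mean squared error is d² + 1/20 + 1/N. That of the paired contrast is 2(1−rho)/n, ignoring selection of who has an RV recording. The paired contrast has the smaller error once d exceeds sqrt(max(0, 2(1−rho)/n − 1/20 − 1/N)). Over rho 0.7 to 0.3 and N 30 to 100, that threshold is 0.34–0.64 SD with 3 pairs, 0.19–0.47 with 5, 0–0.28 with 10 and 0–0.10 with 20.

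**How a shift could look like an effect.** With 10 to 20 LBBAP patients, N of 30 to 100 and no true pacing difference, an assumed shift of 0.5 SD would give a nominal two-sided 5% result in 27% to 53% of such studies (two-sample t-test, noncentral t). The plan sets no 5% rule and nothing in the documents gives the shift, so this shows the mechanism only.

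**Very few pairs.** The highest confidence attainable by a signed-rank interval is 1 − 2/2^n: 93.75% with 5 pairs and 96.9% with 6. A paired-t interval can be computed below 6 pairs, but the table shows that it is very wide, and it then leans on normality.

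**The case against.** The strongest reply is that this is an omission in a small exploratory study and not an error. Nothing in the plan forbids the contrast, and the RV values would appear in the summary tables. Other recorded states, such as fusion pacing at different AV delays, have no explicit contrast either. All of this is true and limits the weight of the point. Still, separate summaries of RV pacing and LBBAP give neither the paired difference nor its spread, and both are useful for planning the next study.

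A reader might infer that the statistics section commits the team to unpaired tests. It does not. The two named non-parametric examples are unpaired, but t-tests can be paired, and the list is open-ended and left to judgement. Paired methods are allowed; what is missing is an in-study RV contrast to apply them to.

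A reader might also infer that the historic comparison is known to be biased. The documents do not show that. Only the title of the cited source can be seen, and section 4.8 does not say which comparison would inform the larger study.

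Finally, RV recordings carry no minimum number, and section 4.2.2 also admits His-bundle systems with an LV lead, so LBBAP patients may number fewer than 20. The upper end of the parity range, 26 pairs, exceeds the whole planned sample. This objection stands, and it is why the paired contrast cannot replace the historic comparison.

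**Conclusion.** The point holds as an inexpensive improvement. The text is clear that RV pacing is to be recorded beside LBBAP where possible, that no endpoint or listed comparison contrasts the two within patients, and that the RV comparator comes only from prior data. The consequence is much less certain: the size and direction of any case-mix effect cannot be determined from the documents, and the harm is indirect, through the planning of a later study.

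Under the assumed inputs, the paired interval matches the historic one only with about 10 to 26 pairs, which may not be reachable. The value of pairing is that it removes between-study case mix, not that it is sure to be more precise. It does not remove selection of the patients who have an RV recording. The illustrative rejection rates rest wholly on assumptions and should not be used to judge how serious the point is.

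**What to change.** In section 4.8, add an exploratory within-patient contrast of LBBAP with RV pacing for SDAT, LVAT and QRS duration, in every LBBAP patient who has an RV recording.

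- Since several LBBAP configurations are recorded, state in advance which one enters the pair.
- Report the mean or median paired difference with a 95% interval (paired t or Wilcoxon signed-rank) and the number of pairs.
- Report the pacing indication of patients with and without an RV recording, so that selection can be seen.
- With fewer than 6 pairs, list the individual differences: a paired-t interval is then very wide and depends on normality, and a signed-rank 95% interval does not exist.
- Keep the historic RV and biventricular comparison, show it beside the paired contrast, and label it as between-study and open to case-mix differences.

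The cost is a few sentences and one added summary of recordings already planned. Endpoints, procedures and sample size do not change. The downside is that the RV subset may be small and selected, and its result applies to that subset only.

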#### **4.7 Secondary Endpoints**

There are no secondary endpoints.

#### **4.8 Statistics**

Summary tables of descriptive statistics will be provided for all variables. Continuous variables will be summarized using means and standard deviations or median and interquartile ranges (IQR), depending on distributional assumptions. Categorical variables will be summarized using percentage and frequency counts. The descriptive statistics will be reported for Baseline and follow-up (adverse events only will be collected).

Analysis of the following objectives will be accomplished using the Chi-square or Fisher's exact tests, and T-tests or non-parametric test (Median test, Wilcoxon rank sum test, etc.), as appropriate.

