## **4.2 Study Population**

### **4.2.1 Approximate Number of Subjects**

Approximately 20 patients will participate in the ECG Belt study to be conducted at Geisinger Heart Institute.

All patients will share the same recruitment process, inclusion and exclusion criteria and same procedures.

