## 4.5 Procedures

The ECG Belt study methodology is composed of:

- 1 scheduled clinic visits (baseline)
- 1-week follow-up monitoring period for adverse events (phone call).

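### Four of the five primary endpoints are within-patient comparisons, but section 4.8 names only independent-group non-parametric tests and plans no within-patient change or its SD

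*Combined protocol and SAP*

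**What the plan says.** Section 4.6 lists five primary endpoint bullets. The first is "ECG Belt analysis of Standard Deviation of Activation Times (SDAT) of LBBAP compared to native conduction". The second compares LVAT under LBBAP with baseline, and the third compares SDAT and LVAT under HOT-CRT with baseline. The fourth is "ECG belt analysis of QRS duration at baseline compared to various LBBAP options". The fifth is a comparison with historical biventricular or RV pacing data.

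Section 4.1 describes how the states are obtained: "ECG belt would be used to record ECG during baseline rhythm, LBBAP in unipolar and bipolar configurations", and/or during HOT-CRT. Section 4.2.1 describes one cohort of about 20: "All patients will share the same recruitment process, inclusion and exclusion criteria and same procedures". Section 4.5 provides a single clinic visit and lists native conduction beside the paced states in both the LBBP and the HOT-CRT recording sequences.

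Section 4.8 gives chi-square or Fisher's exact tests, then "T-tests or non-parametric test (Median test, Wilcoxon rank sum test, etc.), as appropriate". Continuous variables are to be summarised by mean and SD or by median and IQR. On timing it says: "The descriptive statistics will be reported for Baseline and follow-up (adverse events only will be collected". The section adds that the study is not designed for hypothesis testing and that its results will inform the design of a larger study. QRS duration has no line of its own in the list of analyses there.

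**The concern.** Each patient serves as his or her own control in four of the five primary comparisons. The median test and the Wilcoxon rank sum test treat the two sets of readings as coming from different people, and so does an unpaired t-test. When readings in the same patient are positively correlated, such an analysis discards information: the interval for the difference is too wide and the test is conservative. It does not create false positives.

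The planned summaries have the same gap. Follow-up holds adverse events only, so every rhythm state falls under Baseline, and no change between states is specified. A within-patient follow-on study would be sized from the SD of the change, which cannot be derived from the separate SDs of the two states. A parallel-group follow-on would need only the separate SDs.

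Because the study disclaims hypothesis testing, what is at stake is precision and usable design inputs, not the validity of a conclusion.

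**Working it through.** **1. Which comparisons are paired**

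| Section 4.6 bullet | Measure | Compared states | Structure |
|---|---|---|---|
| 1 | SDAT | LBBAP, native | Same patients |
| 2 | LVAT | LBBAP, baseline | Same patients |
| 3 | SDAT and LVAT | HOT-CRT, baseline | Same patients |
| 4 | QRS duration | Several LBBAP options, baseline | Same patients, repeated |
| 5 | As above | Historical pacing data | Different patients |

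Both non-parametric tests named in section 4.8 are for independent samples. No paired test, repeated-measures model, change score, or SD or interval of a change appears anywhere in the document.

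**2. Inputs**

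The document gives about 20 patients (section 4.2.1), with no derivation to reproduce. It gives no SD, effect size, error rate or within-patient correlation. The following are therefore assumptions:

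- Correlation ρ from −0.2 to 0.7.
- SDs of the two states equal, or one twice the other.
- 20, 10 or 7 complete pairs. Section 4.2.2 admits patients "with one of the following at Geisinger within the last 5 years" and lists three device types, so not every patient need have every state. Seven is 20/3 rounded, a deliberately low case. A state available in two of three equally frequent types would give about 13 pairs.

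**3. Standard error of the difference, unpaired over paired**

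Ratio = √[(s₁² + s₂²) / (s₁² + s₂² − 2ρs₁s₂)], which is 1/√(1 − ρ) when s₁ = s₂.

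| ρ | −0.2 | 0 | 0.3 | 0.5 | 0.7 |
|---|---|---|---|---|---|
| Equal SDs | 0.91 | 1.00 | 1.20 | 1.41 | 1.83 |
| One SD twice the other | 0.93 | 1.00 | 1.15 | 1.29 | 1.51 |

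At negative ρ the unpaired standard error is too small.

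**4. Width of the 95% confidence interval, unpaired over paired (equal SDs)**

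Multiply the ratio in step 3 by t(0.975, 2n − 2)/t(0.975, n − 1). This factor is 0.967, 0.929 and 0.890 for n = 20, 10 and 7.

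| Pairs | ρ = 0 | 0.3 | 0.5 | 0.7 | Paired narrower if ρ exceeds 1 − factor² |
|---|---|---|---|---|---|
| 20 | 0.97 | 1.16 | 1.37 | 1.77 | 0.06 |
| 10 | 0.93 | 1.11 | 1.31 | 1.70 | 0.14 |
| 7 | 0.89 | 1.06 | 1.26 | 1.63 | 0.21 |

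**5. Consequence for sizing a within-patient follow-on study**

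SD of change = s√[2(1 − ρ)], which is 1.41s, 1.18s, 1.00s and 0.77s at ρ = 0, 0.3, 0.5 and 0.7. Required pairs are proportional to 2(1 − ρ) = 2.0, 1.4, 1.0 and 0.6. A reader who has only s therefore faces a range of 2.0/0.6 = 3.3-fold.

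For example, take a shift of 0.5s, 80% power and two-sided 5%. Then n = 2(1 − ρ)(1.96 + 0.84)²/0.5², which with unrounded quantiles gives 63, 44, 32 and 19 pairs.

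A reported SD of change would itself be imprecise. At 20 pairs its 95% interval runs from √(19/χ²(0.975, 19)) = 0.76 to √(19/χ²(0.025, 19)) = 1.46 times the estimate.

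**6. Check by simulation**

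Twenty correlated normal pairs were simulated with a 0.5 SD shift and two-sided 5% tests. Power was 27% for rank sum and 54% for signed-rank at ρ = 0.5, and 24% and 77% at ρ = 0.7. With no shift, rank sum rejected in about 1% and 0.1% of runs respectively, which confirms that it is conservative rather than anti-conservative.

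**The case against.** The strongest reply is that section 4.8 never commits to an unpaired analysis. Its reference to t-tests covers the paired version, and the non-parametric tests are open-ended examples to be applied where suitable. The same sentence also governs the historical comparison, for which independent-group methods are the right family. This stands: the fault is under-specification with ill-fitting examples, not a decision to ignore pairing. But the historical bullet does not supply a method for the other four.

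A second reply is that silence on a change score does not rule one out. The research team keeps the patient-level file and could compute the SD of change at any time, and that SD is itself aggregate data that could be released. This also stands. However, section 4.9.1 limits the sponsor to aggregate data, and section 6.2 limits presentations and manuscripts in the same way. What is planned for the tables therefore decides what outside readers receive.

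A third reply is that the size rests on assumed correlations. That is correct, and the 3.3-fold figure depends on the range chosen: extending it down to −0.2 gives 2.4/0.6 = 4.0. The seven-pair case is also only illustrative. The missing QRS line is editorial, since the general objective in section 4.8 can be read to cover it.

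**Conclusion.** The concern holds. Four of five primary endpoint bullets are paired, section 4.8 names no method specific to paired data, and no within-patient change or its SD is planned. If an unpaired method were used on 20 pairs with equal SDs, the confidence interval would be 16% to 77% wider than necessary for correlations of 0.3 to 0.7. There would be no loss at zero correlation, and the unpaired standard error would be too small at negative correlation.

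The cost to a follow-on study arises only if that study is within-patient and its designers have just the planned summaries. Nothing here invalidates an exploratory study, but the gap touches most of the primary endpoints and should be closed before analysis.

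**What to change.** In section 4.8:

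- For native or baseline rhythm against LBBAP or HOT-CRT on SDAT, LVAT and QRS duration, name the paired t-test or the Wilcoxon signed-rank test in place of the rank sum and median tests.
- For each comparison, report the number of complete pairs, the within-patient difference, its SD and its 95% confidence interval.
- Where several configurations are recorded per patient, as in the QRS endpoint, allow a model with a patient random effect.
- Add a QRS duration line to the list of analyses.
- Describe the historical comparison separately, using independent-group methods suited to the data obtainable, or summary-based methods if only published means and SDs are available. Independent-group tests also remain available for comparisons between device types.

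The cost is a small change of wording and some programming. No extra recordings, visits or patients are needed.
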